A single large discrete target is displayed filling the entirety of the screen and shrinks to 10pixels for 5 seconds. The target is presented twice. The user under test's fixation radius is scored as a Circular-Error Probable (CEP) size. The smaller the CEP radius, the better the test result.	A set of 13 discrete targets are displayed randomly and twice repeatedly on fixed coordinates for a preset duration of 1 second (adjustable) on the screen for the user under test. Targets are presented in a pseudo-randomly to avoid bias in gaze point detection. An area-of-effect radius is scored if the user's gaze intersects with the presented target.	A set of 13 discrete targets that increases in radius at 10 pixels/second are displayed randomly on fixed coordinates on the screen for the user under test. Targets are presented in a pseudo-randomly to avoid bias in gaze point detection. The target radius is scored if the user's gaze intersects with the presented target at the presented radius size. The smaller the radius, the better the test result.	Subject under test to pursue a generated target moving in a sinusoidal pattern at a speed of 5cm/s.

OCCUTRACK

Methodology

This study aims to determine whether home-based monitoring using the CRYSTALSIGHT gaze-based Hyperacuity Perimetry system, when added to a PRN treatment regimen, is non-inferior to standard care using the Amsler Grid in detecting recurrence of choroidal neovascularisation (CNV) associated with wet age-related macular degeneration (AMD).

Recurrence is defined by a central retinal thickness (CRT) increase of ≥ 50 microns or a loss of best-corrected visual acuity (BCVA) of ≥ 5 letters.

The study also aims to evaluate whether CRYSTALSIGHT enables earlier detection of CNV progression, as reflected by better VA and CRT values at the time of detection, through biweekly self-tests conducted in an unsupervised home setting.

Study Design

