This is a randomised, open-label, non-inferiority clinical trial comparing two parallel arms: a standard care arm using Amsler Grid home monitoring (PRN), and an intervention arm using the CRYSTALSIGHT gaze-tracking system (PRN+). A total of 220 (Singapore – 60, United Kingdom – 80, United States – 80) participants will be randomised in a 1:1 ratio. Participants in the intervention arm will self-administer biweekly CRYSTALSIGHT tests at home, while those in the control arm will use the Amsler Grid. Both arms will attend monthly clinic visits for standard evaluations, including VA, BCVA, and OCT. Alerts generated by the CRYSTALSIGHT system based on deviation thresholds will trigger early clinic recall for confirmatory imaging and potential re-treatment.

[figure not shown]

Figure 4 Details of the home-use clinical trial study design. The trial objective: show that PRN+ is non-inferior to standard of care PRN with better VA/VF outcomes

Development of CRYSTALSIGHT cutoff scores should have been conducted in the cohort-1 1 study [NCT: NCT06518512] (Analysis). This Phase 2 should be the application of validated cut-off scores. The second aim will be to compare the accuracy of CRYSTALSIGHT and Amsler, and sensitivity and specificity check.

In addition to identifying CRYSTALSIGHT visual risk prediction cut-off scores, detection yields, and diagnostic Performance indicators will also be evaluated. Progression to CNV was

OCCUTRACK

determined by the investigator, based on standardised OCT confirmation. At the clinical trial site, these events were confirmed by gradings conducted by masked, certified independent personnel who did not know the treatment assignment. Events from both arms are graded using a standardised protocol.

[figure not shown]

Figure 5 In Cohort 2, home-based score deviation detected, study coordinator will schedule hospital checkup immediately. If CRYSTALSIGHT correctly detects wet AMD recurrence confirmed by OCT, subject exits the study.

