This study will use the CRYSTALSIGHT system in an unsupervised home setting. Participants will perform biweekly self-monitoring with the CRYSTALSIGHT device. The threshold algorithm will be implemented and validated with subjects. Threshold information from Cohort 1 will thus be incorporated into the Cohort 2 intervention measures. Figure 5 illustrates the function of the CRYSTALSIGHT score as the basis for an intervention measure: an earlier-than-expected clinic visit should be scheduled immediately for clinic vision testing and urgent anti-VEGF administration.

Pro Re Nata (PRN): Standard treatment (control arm)

Participants randomized to the standard treatment arm received specific instructions from investigators for self-monitoring of vision at home to detect progression of AMD. Aids such as the Amsler grid. This group is referred to below as the standard treatment group. If participants experienced symptoms, they were instructed to call their clinical centre immediately and schedule an appointment within 72 hours.

PRN+: Home monitoring device (device arm)

In addition to the same standard of care instructions, participants will receive a CRYSTALSIGHT home monitoring device with instructions for installation and use. This arm is referred to below as the device arm. In cases where baseline measurements could not be obtained due to a pre-existing visual field defect in at least one study eye, participants returned the device and continued monitoring with standard treatment only but were still included in the final analyzes in the intent-to-treat (ITT) cohort as part of the device arm.

Participants were encouraged to use the device twice a week, and results were automatically transmitted via internet cloud to a Occutrack's data monitoring center. If testing of the device indicated a change from baseline measurements, an alert was sent from the monitoring center to the participant's clinical center, prompting staff to schedule an appointment with the study ophthalmologist within 72 hours.

This study is an open-label, randomized study designed to evaluate the safety and efficacy of the CRYSTALSIGHT device when used by patients in their own homes. The study will

OCCUTRACK

recruit a group of patients who meet certain eligibility criteria and provide them with the CRYSTALSIGHT device for use at home.

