- Maintenance Monitoring:** Once the participant has achieved a nominal baseline level of visual performance, the system will remind the participant to regularly monitor their visual performance with the CRYSTALSIGHT device at the scheduled frequency.

OCCUTRACK

6. **Follow-up:** The PI will schedule regular follow-up appointments to monitor the participant's progress and adjust monitoring frequency as needed.

It is important to note that CRYSTALSIGHT does not work for all participants and it may take several months to detect disease relapse.

Study Schedule Table

Baseline Visit #1 Month 1	
Standard Routine Care
 
 • Visual Acuity (VA) • BCVA (Optional) • Optical Coherence Tomography (OCT) • Colour Fundus Photography • Clinical Consultant Review • Intravitreal Injections (IVT) 
Research Procedure
 
 • CRYSTALSIGHT Eye Gaze Tracking for investigative arm and insurance of CRYSTALSIGHT device for home monitoring. 
OR
 
 • Amsler Grid for Amsler Grid arm
Follow Up Visit #2 Month 2 (+/- Four weeks)	
Standard Routine Care
 
 • Visual Acuity (VA) • BCVA (Optional) • Optical Coherence Tomography (OCT) • Colour Fundus Photography • Clinical Consultant Review • Intravitreal Injections (IVT) (Optional)
Follow Up Visit #3 Month 3 (+/- Four weeks)	
Standard Routine Care
 
 • Visual Acuity (VA) • BCVA (Optional) • Optical Coherence Tomography (OCT) • Colour Fundus Photography • Clinical Consultant Review • Intravitreal Injections (IVT) (Optional)
Follow Up Visit #4 Month 4 (+/- Four weeks)	
Standard Routine Care
 
 • Visual Acuity (VA) • BCVA (Optional) • Optical Coherence Tomography (OCT) • Colour Fundus Photography • Clinical Consultant Review • Intravitreal Injections (IVT) (Optional)

OCCUTRACK

Follow Up Visit #5 Month 5 (+/- Four weeks)	Standard Routine Care 
 • Visual Acuity (VA) • BCVA (Optional) • Optical Coherence Tomography (OCT) • Colour Fundus Photography • Clinical Consultant Review • Intravitreal Injections (IVT) (Optional)
Follow Up Visit #6 Month 6 (+/- Four weeks)	Standard Routine Care 
 • Visual Acuity (VA) • BCVA (Optional) • Optical Coherence Tomography (OCT) • Colour Fundus Photography • Clinical Consultant Review • Intravitreal Injections (IVT) (Optional)

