Follow Up Visit #7 Month 7 (+/- Four weeks)	Standard Routine Care 
 • Visual Acuity (VA) • BCVA (Optional) • Optical Coherence Tomography (OCT) • Colour Fundus Photography • Clinical Consultant Review • Intravitreal Injections (IVT) (Optional)
Follow Up Visit #8 Month 8 (+/- Four weeks)	Standard Routine Care 
 • Visual Acuity (VA) • BCVA (Optional) • Optical Coherence Tomography (OCT) • Colour Fundus Photography • Clinical Consultant Review • Intravitreal Injections (IVT) (Optional)
Follow Up Visit #9 Month 9 (+/- Four weeks)	Standard Routine Care 
 • Visual Acuity (VA) • BCVA (Optional) • Optical Coherence Tomography (OCT) • Colour Fundus Photography • Clinical Consultant Review • Intravitreal Injections (IVT) (Optional)
Follow Up Visit #10 Month 10 (+/- Four weeks)	Standard Routine Care 
 • Visual Acuity (VA) • BCVA (Optional) • Optical Coherence Tomography (OCT) • Colour Fundus Photography • Clinical Consultant Review

OCCUTRACK

Follow Up Visit #11 Month 11 (+/- Four weeks)	Standard Routine Care 
 • Visual Acuity (VA) • BCVA (Optional) • Optical Coherence Tomography (OCT) • Colour Fundus Photography • Clinical Consultant Review
Study Exit Visit #12 Month 12 (+/- Four weeks)	Standard Routine Care 
 • Visual Acuity (VA) • BCVA (Optional) • Optical Coherence Tomography (OCT) • Colour Fundus Photography • Clinical Consultant Review • Intravitreal Injections (IVT) (Optional)

Locations

Three study sites are proposed:

1. [name], PLLC, New London, United States
2. The Princess Alexandra Eye Pavilion in Edinburgh, Scotland, United Kingdom
3. Tan Tock Seng Hospital, Singapore

Timeframe

Estimated Start Date: June, 2025

Estimated Completion Date: August, 2026

Eligibility

Inclusion / exclusion criteria of this study are as follows.

Participation Requirements:

Genders: Both

Minimum Age: 55

Healthy Volunteers: No

Inclusion criteria

1. Subjects in the age group ≥ 55 to 99 years old.
2. Both genders
3. Able to understand verbal spoken instructions in British/American English, Chinese or Bahasa Melayu and demonstrate device functionality and implementation.
4. Able to turn on and connect the CRYSTALSIGHT device to a computer independently or with the help of family.

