4. Follow best practices: The participant should follow best practices when using the device, including placement, head position, and attention to stimulation targets on the screen.

By following these steps, a new user can master the CRYSTALSIGHT health monitoring device and effectively manage their AMD condition.

How are they going to get the device

One CRYSTALSIGHT boxed unit will be signed over to the study participant to bring home after the recruitment administration is done during the regular clinic check-up and when the participant has agreed and signed the Informed Consent Form (ICF) to be included in the study.

System reminders

A study coordinator will monitor the electronic records system and will call the participant to conduct a self-test at home if they miss the test by 1 day. A system

OCCUTRACK

reminder will automatically send a message and email to remind the user to take the test if a scheduled self-test is missed by a day.

Results and reporting: The results of the tests will be transmitted to a secure server where they will be analyzed by the principal investigator and study coordinator. If any changes in vision are detected, the subject will be contacted by the study coordinator and a follow-up appointment will be scheduled.

Sample size calculation:

According to the workflow, all participants will have routine visits to clinic with OCT scans performed once every 4 weeks. Participants randomised into the CRYSTALSIGHT group will have measurements taken twice a week if the testing results are all negative. In case of a positive result with CRYSTALSIGHT, another test will be done on the next day. Participants will be recalled for review after two consecutive positive results are presented. Depending on the pathology presented on the OCT scan, IVT may be given for disease management. On the other hand, participants randomised into the Amsler Grid group will be evaluated by Amsler Grid and by OCT.

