For participants in the CRYSTALSIGHT group, each participant will have a testing result by CRYSTALSIGHT and by OCT every 4 weeks or less if the positive result triggers a clinical visit. The result is considered correct if it is consistent with the findings of the OCT scan. During the one-year study period, the total number of correct results generated by CRYSTALSIGHT will be counted and the accuracy for these participants will be calculated as number of correct results divided by the total number of clinical visit. For participants in the Amsler Grid group, the accuracy for each participant will also be calculated.

According to literature, the accuracy of Amsler Grid in detecting disease activity was about 80%, we will assume that CRYSTALSIGHT has the same accuracy. For the Singapore population, we will also assume that standard deviation of the accuracy to be 0.12 and setting the maximum allowable difference in accuracy (non-inferiority margin) between the two groups to be 0.09, with one-sided type 1 error of 0.025 and a power of 0.8, a total of 52 participants will be required (26 per group). Considering of 15% attrition rate, a total of 60 participants will be required.

For global study, we assume a higher standard deviation of the accuracy to be 0.21 and a dropout rate of 21%, a total of 220 participants will be required (110 per group).

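### The four-week tolerance either side of each monthly visit permits follow-up OCTs 0 to about 12 weeks apart, so the schedule does not ensure the four-weekly OCT stated elsewhere in the protocol

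*Protocol*

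**What the plan says.** Protocol, Study Schedule Table: visits 2 to 12 are one month apart, OCT is listed at each, and each carries the same tolerance, for example "Follow Up Visit #3 Month 3 (+/- Four weeks", from visit 2 through "Study Exit Visit #12 Month 12 (+/- Four weeks". The baseline visit has no tolerance.

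Three other statements give the intended frequency:

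- Study Design: "Both arms will attend monthly clinic visits for standard evaluations", and OCT is among those evaluations.
- Sample size calculation: "all participants will have routine visits to clinic with OCT scans performed once every 4 weeks".
- Sample size calculation, for the device group: "a testing result by CRYSTALSIGHT and by OCT every 4 weeks or less", where the shorter interval refers to a visit brought forward by a positive result.

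The same section builds the accuracy measure on these visits. A result is correct if it agrees with OCT, and "the accuracy for these participants will be calculated as number of correct results divided by the total number of clinical visit". The Methodology section judges earlier detection "as reflected by better VA and CRT values at the time of detection".

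The protocol sets no hard minimum or maximum gap between visits and no rule for a visit that falls inside two windows. The follow-up step under Recruitment lets the investigator change the monitoring frequency, without limits.

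**The concern.** A visit window defines which dates count as compliant. Here the half-width equals the spacing, so a visit may take place on the target date of the visit before it or after it and still be in window. A long gap without OCT would not be recorded as a deviation from the table, although it departs from the monthly and four-weekly frequency stated elsewhere.

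This matters because OCT is the reference standard. Symptoms in either arm bring an early visit: for the control arm the protocol says "If participants experienced symptoms, they were instructed to call their clinical centre immediately and schedule an appointment within 72 hours", and the device arm receives the same standard instructions. Device alerts bring a further early visit in the device arm. A recurrence with neither is found only at the next scheduled OCT. For such an eye the visit gap decides when the recurrence is found and when treatment can start. It also sets the VA and CRT recorded at detection. At the other extreme, two visits close together enter nearly the same eye state twice in the participant's accuracy, because every clinic visit counts equally.

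**Working it through.** **Inputs.** Tolerance w = 4 weeks each side (Study Schedule Table). Spacing s = one month. The protocol does not define a month, so both readings are shown: s = 4 weeks, as in the sample size section, and a calendar month, s = 365.25/12/7 = 4.35 weeks. The tolerance is taken around the scheduled date, because the table attaches it to the month number.

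**The plan's own figure.** With every visit on its target date, the gap is s = 4 or 4.35 weeks. The stated frequency is therefore reproduced by the window centres.

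**What the tolerance permits.**

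| Quantity | Formula | 4-week month | Calendar month |
|---|---|---|---|
| Full window width | 2w | 8 weeks | 8 weeks |
| Overlap of adjacent windows | 2w - s | 4.0 weeks (50%) | 3.7 weeks (46%) |
| Shortest follow-up gap | max(0, s - 2w) | 0 | 0 |
| Longest follow-up gap | s + 2w | 12.0 weeks | 12.3 weeks |
| Baseline to visit 2 | s - w to s + w | 0 to 8.0 weeks | 0.3 to 8.3 weeks |
| One visit 2 weeks early, next 2 weeks late | s + 4 | 8.0 weeks | 8.3 weeks |
| Longest total of two consecutive gaps | 2s + 2w | 16.0 weeks | 16.7 weeks |
| Planned total of two gaps | 2s | 8.0 weeks | 8.7 weeks |

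The untruncated lower limit s - 2w is negative (-4.0 or -3.7 weeks), so the windows alone do not even fix the order of two adjacent visits.

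The 12-week gap is the extreme. It needs one visit a full four weeks early and the next a full four weeks late. It cannot occur twice running: two consecutive gaps total at most 16 weeks, for example 12 + 4 or 8 + 8.

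If the tolerance were instead counted from the previous actual visit, each gap would run from s - w to s + w, that is 0 to 8.0 or 0.3 to 8.3 weeks. That is still up to about twice the stated interval.

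**Windows that would work.** Adjacent windows do not overlap when 2w < s, that is w below 2 weeks on the 4-week reading. With w = 1, the gap is s - 2 to s + 2 = 2 to 6 weeks, or 2.3 to 6.3 with calendar months. Baseline to visit 2 is then 3 to 5, or 3.3 to 5.3 weeks.

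**Sample size.** The calculation uses the SD, margin, error rate, power and attrition. The visit window enters none of these, so the stated totals do not change.

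**The case against.** The strongest reply is that the table is not the only scheduling text. The protocol states monthly visits and four-weekly OCT, and the target dates agree with both, so a site that keeps to them scans about every four weeks. A reader might infer from the window that the schedule cannot deliver four-weekly OCT, or that the protocol states no interval at all. Neither is supported. The interval is stated; the tolerance fails to secure it. What remains is a conflict: a 12-week gap satisfies the table and breaches the other statements, and nothing says which governs.

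A second reply is that these are routine-care appointments in three countries, so some tolerance is reasonable. That stands as a reason for having a window, but not for one as wide as the spacing on each side. Nothing in the documents singles out +/- 1 week among windows below 2 weeks; it is an example.

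Third, the link to the accuracy endpoint is thin. The device is used twice weekly, so a recent test should exist whenever the OCT falls, and agreement at a visit does not need equal gaps. This largely stands. A reader might go further and infer a biased comparison or lost power. The documents do not support that: the window is the same in both arms, no sample size input depends on it, and the number of scheduled OCTs is unchanged. The trial is open-label, so visit timing could in principle differ by arm, but nothing in the protocol shows that it would.

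Fourth, the late-detection harm concerns only recurrences with neither symptoms nor an alert, and the protocol gives no figure for how common these are. That is correct and limits the point. Even so, the protocol itself says that high-risk patients often do not use the Amsler grid between visits and that the device does not suit every participant. Scheduled OCT is therefore a backstop that matters.

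Finally, assigning visits to overlapping windows can be left to a statistical analysis plan. The window itself governs site conduct, however, and no analysis rule can recover an OCT that was not taken on time.

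**Conclusion.** The point holds as a conflict between a stated frequency and the tolerance around it. The table permits follow-up OCTs 0 to about 12 weeks apart (12.0 or 12.3 by the definition of a month), with adjacent windows overlapping by 50% or 46%. Modest shifts of two weeks each way already double the interval.

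The figures rest on windows centred on the scheduled dates and describe what is permitted. How often long or very short gaps would occur cannot be estimated from the protocol. The consequence is confined to OCT timing: possible late discovery of silent, unalerted recurrences, with its effect on VA and CRT at detection and on patient care, and possible near-duplicate scoring when visits bunch. This is a cheap improvement to the protocol; it does not undermine the primary comparison.

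**What to change.** In the Study Schedule Table, replace the four-week tolerance for visits 2 to 12 with a non-overlapping window under +/- 2 weeks of the scheduled date, for example *+/- 1 week*.

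In the sample size section, change the sentence on routine OCT to *every 4 weeks (+/- 1 week)*. Change the sentence on the device group to *every 4 weeks (+/- 1 week), or earlier if an alert triggers a visit*.

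The edit covers the table entries and two sentences and leaves the sample size alone. Sites keep a two-week booking range per visit, but they lose flexibility and will record more visit deviations.

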5. Subjects undergoing treatment for Wet-AMD without any signs and symptoms of recurrence of active AMD (AMD recurrence: choroidal neovascularisation,

OCCUTRACK

intraretinal or subretinal fluid is present) with OCT lesion fluid volume more than 2 mm² or ILM height more than 300µm.

6. Ability to comply with the study protocol, in the investigator's judgment.
7. Subjects must be able to understand and provide informed consent. A signed informed consent form must be provided before any study assessments.

Exclusion criteria

1. Unable to understand verbal spoken instructions and demonstrate device functionality and implementation.
2. Unable to turn on and connect the CRYSTALSIGHT device to a computer independently.
3. Any ocular surgery in the previous 3 months, or vitrectomy in the previous 12 months
4. Any history of macular pathology unrelated to AMD affecting vision or contributing to the presence of intraretinal or subretinal fluid in the study eye
5. Any concurrent intraocular condition in the study eye that, in the opinion of the investigator, could either reduce the potential for visual improvement or require medical or surgical intervention during the study
6. Any prior or concomitant treatment for CNV or vitreomacular-interface abnormalities in the study eye.
7. History of idiopathic or autoimmune-associated uveitis in either eye
8. Active ocular inflammation or suspected or active ocular or periocular infection in either eye.

Study population: patients with recurrent vision problems diagnosed with active Wet-AMD at TTSH eye clinics.

Pre-specified clinical outcome: The prespecified adverse clinical outcome used in this study will be the **recurrence of Active Wet AMD**, which will be identified by an increase in central retinal thickness (CRT) of at least 50 microns or a loss of best-corrected VA of 5 letters or more.

Training

To prepare for home use of the CRYSTALSIGHT device, the following processes are performed in the clinic:

- The examining physician or study coordinator will unpack a CRYSTALSIGHT training unit for the patient to help the patient understand the device and ensure that the home user understands the device, its purpose, and how it works. Instructions on how to set it up at home include connecting the device to a laptop with an Internet connection.

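### Inclusion criterion 5 contradicts itself on disease activity at entry, and conflicts with the study population line and exclusion criterion 6

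*Protocol*

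**What the plan says.** All the operative text is in the Eligibility section of the Protocol.

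- **Inclusion criterion 5, state required:** "Subjects undergoing treatment for Wet-AMD without any signs and symptoms of recurrence of active AMD". A bracket then explains recurrence as the presence of CNV or of intraretinal or subretinal fluid.
- **Inclusion criterion 5, thresholds:** the sentence continues after the bracket with "OCT lesion fluid volume more than 2 mm² or ILM height more than 300µm".
- **Study population:** "patients with recurrent vision problems diagnosed with active Wet-AMD at TTSH eye clinics".
- **Exclusion criterion 6:** "Any prior or concomitant treatment for CNV or vitreomacular-interface abnormalities in the study eye".
- **Pre-specified clinical outcome:** recurrence of active wet AMD, identified by "an increase in central retinal thickness (CRT) of at least 50 microns or a loss of best-corrected VA of 5 letters or more". Study Objectives and Methodology give the same change-based rule.

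The Protocol does not define the fluid measure or ILM height anywhere else, and does not say how either relates to CRT.

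**The concern.** The trial asks how well home monitoring detects recurrence, which presupposes that the disease is quiet at entry. The criterion meant to secure this joins an absence condition to two thresholds that run upwards, and does not say what the thresholds apply to. The neighbouring population line and exclusion 6 pull in other directions. Investigators at three sites in three countries would each have to settle the meaning for themselves.

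At stake is the starting state of the participants. The device raises an alert on a deviation from the participant's own baseline (10 points, in the description of the intervention phase). Under Sample size calculation, a test result counts as correct when it agrees with the OCT at the visit. Both depend on what the eye looked like at entry.

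**Working it through.** No sample size, power or error-rate figure enters this point, so there is nothing to recompute. The check sets the passages side by side.

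**1. Who is admitted under each reading of criterion 5.** Let F be the fluid measure, with threshold 2 in whatever unit is meant, and H the ILM height in µm. Assume no sign of CNV other than fluid.

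- Reading A: the thresholds describe the patient. Admit if there is no fluid and (F > 2 or H > 300).
- Reading B: the thresholds qualify the recurrence being ruled out. Refuse if fluid is present with F > 2 or H > 300.
- Bracket alone: refuse if any fluid is present.

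| Eye at entry | Reading A | Reading B | Bracket alone |
|---|---|---|---|
| No fluid, H ≤ 300 | refused | admitted | admitted |
| No fluid, H > 300 | admitted | admitted, or refused if height alone counts as recurrence | admitted |
| Fluid, F ≤ 2 and H ≤ 300 | refused | admitted | refused |
| Fluid, and F > 2 or H > 300 | refused | refused | refused |

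Under A the fluid threshold can never be met, because no fluid is allowed; only thick, dry retinas qualify. Under B the third row is admitted although the bracket counts it as recurrence. A and B give opposite answers in the first and third rows.

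**2. Against the population line.** That line describes active disease. Taken at face value it points to the third and fourth rows, whereas the opening words of criterion 5 point away from them.

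**3. Against exclusion 6.** Criterion 5 requires treatment for wet AMD. Exclusion 6 removes anyone with earlier or current CNV treatment in the study eye. The Study Schedule Table also lists intravitreal injection at the baseline visit. For a study eye treated for wet AMD, criterion 5 and exclusion 6 cannot both be applied as written.

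**4. The unit.** A volume needs a cubic unit, and mm² measures area. The Protocol gives no conversion. A superscript 3 misread as 2 when the text was extracted cannot be excluded. Steps 1 to 3 do not depend on the unit.

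**5. What follows for measurement.** If an eye with fluid is enrolled, its device baseline is recorded during activity, so a later alert is a deviation from an already abnormal reference. If the OCT finding at a visit is judged by the presence of fluid, the OCT can be positive from the first visit without any new event. The Protocol does not fix which OCT finding makes a result correct, so the size of this effect cannot be worked out.

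**The case against.** The strongest reply is that the intention is clear enough. A page header splits the sentence, and reading B is the natural one. Other sections support an entry state of treated, currently quiet disease: the Study Summary and the description of phases speak of patients coming off anti-VEGF injections, and Recruitment of patients on a treatment regimen. The population line may record diagnostic history. The unit may be an extraction artefact or one wrong word, and the height threshold has a valid unit. Allocation is randomised 1:1, so the mix of entry states should be similar in the two arms on average.

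Much of this stands. Reading B is more plausible, the unit cannot carry the point alone, and no directional bias between arms has been shown. But reading B still admits fluid that the bracket counts as recurrence, and none of this reconciles exclusion 6 with criterion 5. Balance between arms does not turn disease already present into a recurrence.

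Three stronger inferences are tempting, and the Protocol does not support them:

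- *That the entry rule must equal the outcome rule.* Entry describes a state at one time and the outcome a change, so they may properly differ. Examples such as 290 to 310 µm (past the entry height, but a rise of only 20 µm) assume that ILM height is comparable to CRT, which the Protocol never says. They also use the entry rule after entry, where the Protocol does not apply it.
- *That an eye active at entry scores at once as a recurrence.* The pre-specified outcome needs a 50-micron rise or a 5-letter loss, and activity at entry alone cannot meet it.
- *That the sites will enrol different populations.* They could; nothing in the document shows that they will.

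**Conclusion.** The point holds as a defect in an operative eligibility rule. Criterion 5 is internally contradictory on one reading and at odds with its own bracket on the other, and it conflicts with the population line and exclusion 6. Eyes with active disease could be enrolled, which would weaken the trial's ability to measure detection of recurrence.

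The size is unknown: neither the share of participants affected nor the direction of any between-arm bias can be computed from the Protocol. The conclusion rests on the wording of criterion 5, the population line and exclusion 6, and would stand if the unit proved to be mm³. The consequence for accuracy also assumes that some sites take a reading that lets active eyes in. This should be corrected, but it does not by itself invalidate the design. A statistical analysis plan would not repair it, because the Protocol fixes eligibility.

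**What to change.** - Rewrite criterion 5 as two statements: the disease state required at entry, and the OCT thresholds that establish it. Give each threshold its direction (at or below, or above) and a unit that matches the quantity.
- State whether any fluid disqualifies, or only fluid beyond the threshold.
- Reconcile the result with the study population line and exclusion 6, making clear which eye and which treatment each refers to.
- Use distinct terms for activity at entry and for the change-based outcome, or state how the two relate. They need not be identical.

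The thresholds and the clinical rule are for the sponsor to settle; none is proposed here.

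The cost is a protocol amendment. The Timeframe section gives an estimated start of June 2025. If recruitment has begun, the entry state of everyone already enrolled should also be checked against the clarified rule. The planned analysis itself need not change.
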